### Secondary clinical efficacy assessments

- Percent of subjects requiring autografting of the StrataGraft treatment site by 3 months
- Incidence of complete wound closure of the treatment sites at 3, 6, and 12 months
- Percent wound closure at 3, 6, and 12 months
- Cosmesis of treatment sites at 3, 6, and 12 months
- Cosmesis of donor sites at 3, 6, and 12 months
- Pain of donor sites measured at days 3, 7, 14, 21, and 28

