Stratatech has completed STRATA2001, a first-in-human, dose escalation trial evaluating the safety of StrataGraft skin tissue in subjects with complex skin defects of 5-73% total body surface area (TBSA) resulting from thermal injury, trauma, or necrotizing fasciitis. This study showed that autograft take in wound beds temporized with StrataGraft skin tissue was comparable to autograft take in wounds temporized with cadaver allograft. No product-related adverse events (AE) were seen following application of StrataGraft skin tissue to the full-thickness component of these complex skin defects for seven days. There was no change in the types of AE as the total

---

dosage of StrataGraft skin tissue increased 5-fold across the three cohorts from 44 cm^2 to 220 cm^2. StrataGraft skin tissue remained intact and viable throughout the seven day placement period, suggesting the potential for continued biological activity during longer exposure.

The STRATA2011 study, a follow-up to the STRATA2001 trial, has been conducted as an open-label, dose-escalation, multicenter study evaluating the safety, tolerability, and efficacy of prolonged exposure to increasing dosages of a single application of StrataGraft skin tissue in promoting the healing of complex skin defects with intact dermal elements. In STRATA2011, a single application of StrataGraft tissue was applied to the deep partial-thickness portion of thermal burns and left in place to evaluate whether StrataGraft could promote autologous tissue regeneration thereby reducing or eliminating the need for the surgical harvesting of a donor site for autografting.

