The STRATA2014 study builds upon the data generated in the STRATA2001 and STRATA2011 studies in the same patient population as that for STRATA2001. The proposed study is designed as an open-label, controlled, randomized, multicenter, dose-escalation study evaluating the safety, tolerability, and efficacy of single or multiple applications of StrataGraft skin tissue as an

alternative to donor site harvesting and autografting in promoting the healing of full-thickness complex skin defects. The proposed study population will include subjects with up to 49% TBSA complex skin defects including a full-thickness component. Targeted enrollment for this study is up to 20 subjects with full-thickness complex skin defects requiring surgical excision and autografting. Subjects will be sequentially enrolled in two cohorts of increasing dosage of StrataGraft skin tissue (treatment area per surgical application). Subjects will be eligible to receive up to three applications of StrataGraft skin tissue in the treatment of full-thickness skin defects. In the first cohort, up to 10 subjects will receive an initial surgical application of up to 200 cm^2 of StrataGraft skin tissue. The second cohort will enroll up to 10 subjects who will receive an initial treatment of up to 400 cm^2 of StrataGraft skin tissue. The treatment site will be evaluated to assess the progress of wound healing. Per the clinical judgment of the Clinical Investigator and as necessary to promote complete wound closure, wounds may be treated with up to two additional applications StrataGraft tissue. The cumulative study dosage for cohort 1 may be up to 600 cm^2 and for cohort 2 may be up to 1200 cm^2.

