Two comparable wounds in each subject will be identified and the wounds randomized to receive StrataGraft skin tissue or a surgically harvested autologous skin graft. The inpatient comparator design allows for a matched control to eliminate significant underlying immunologic, physiologic, and scarring variables inherent in this population. Two donor sites will be prospectively designated to provide a source of autograft skin for the control treatment site and, if needed, the StrataGraft treatment site. Both the StrataGraft skin tissue and autograft control will be placed on the treatment sites immediately following surgical excision of non-viable tissue. After the fifth subject in cohort 1 reaches the three month study session, an interim safety report will be generated and reviewed by the Data and Safety Monitoring Board (DSMB). Progression to cohort 2 will take place only after a favorable review of the safety information by the DSMB.

Efficacy will be assessed by evaluating the percent area of the StrataGraft treatment site requiring autografting by 3 months, pain of the donor sites through day 28, and the incidence of complete wound closure at three months supported by clinical photography. Cosmesis of the treatment sites will be evaluated at 3, 6, and 12 months. Additional assessments will include persistence of allogeneic DNA in the StrataGraft-treated sites as well as cosmesis and pain of the donor sites. Safety assessments will include monitoring of AE, vital signs, laboratory safety values, incidence of wound infection, and immunologic responses to StrataGraft tissue.

In addition to routine safety monitoring by the study's medical monitor (MM) and the DSMB, the study will have a Department of Defense (DoD) research monitor whose sole responsibility will be to assess safety. The decision to advance to cohort 2 will be based on an interim safety analysis by the DSMB after the fifth subject in the first cohort has completed the 3 month visit. This time frame will allow for the evaluation of acute, sub-acute, and early chronic AE resulting from prolonged exposure and multiple applications of StrataGraft skin tissue in these subjects. Enrollment into the second cohort will begin only after the DSMB has reviewed the interim safety data and recommended progression. A copy of the interim analysis will also be submitted to the Investigational New Drug (IND) on file for StrataGraft skin tissue.

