## **STUDY DESIGN**

### **Primary clinical endpoints**

- Percent area of the StrataGraft treatment site requiring autografting by 3 months
- Wound closure of the treatment sites at 3 months

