### Study Assessments (efficacy)

Assessments	Methods	Schedule of Assessments
Percent area of treatment site requiring autografting	Clinician assessment supported by photodocumentation	Days 3, 7, 14, 21, 28 and 3 months
Wound closure of treatment sites	Clinician assessment supported by photodocumentation	3, 6, and 12 months
Cosmesis of treatment sites	POSAS supported by photodocumentation	3, 6, and 12 months
Cosmesis of donor sites	POSAS supported by photodocumentation	3, 6, and 12 months
Pain of donor sites	Wong-Baker FACES pain rating scale (FPRS)	Days 3, 7, 14, 21, and 28

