## TEST PRODUCT ROUTE OF ADMINISTRATION AND DOSE REGIMEN

Two full-thickness wound areas of comparable depth and area (contiguous or non-contiguous with each other) on the arms, legs, or torso in subjects with complex skin defects will be prospectively identified as treatment sites A and B. Treatment site A will always be anterior, superior/proximal, lateral or to the subject's right. Treatment site B will always be posterior, inferior/distal, medial or to the subject's left. After excision, the two sites will be randomized to be treated with StrataGraft skin tissue or autograft. Each treatment site must be a single contiguous full-thickness wound area. Any wound outside the study treatment sites will be treated according to the institutional standard of care for that wound.

Subjects in cohort 1 may receive an initial dosage of up to 200 cm^2 each of StrataGraft skin tissue and autograft. Subjects in cohort 2 may receive an initial dosage of up to 400 cm^2 each of StrataGraft skin tissue and autograft. StrataGraft skin tissue is to be meshed 1:1 prior to application. Autograft may be meshed up to 4:1 as per SOC prior to application.

Subjects in both cohorts are eligible to receive up to two additional applications of StrataGraft skin tissue days 6 through 31, inclusive at the discretion of the Clinical Investigator as deemed clinically necessary to promote complete wound closure. The subsequent applications of StrataGraft tissue will be applied to wounds after surgical or non-surgical debridement of the wound areas consistent with standard practice.

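### Does scoring wound closure only from 3 months onward leave the comparison of StrataGraft with autograft deficient?

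*Combined protocol and SAP*

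**What the plan says.** The combined protocol and SAP names three closure endpoints. Under Primary clinical endpoints it lists "Wound closure of the treatment sites at 3 months". Under Secondary clinical efficacy assessments it lists the incidence of complete closure at 3, 6 and 12 months, and "Percent wound closure at 3, 6, and 12 months". The closure row of the Study Assessments (efficacy) table repeats 3, 6 and 12 months.

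Earlier visits exist. The same table schedules the area requiring autografting at "Days 3, 7, 14, 21, 28 and 3 months", by clinician assessment with photographs. As an endpoint, however, this is defined for one arm: the Study Rationale speaks of "evaluating the percent area of the StrataGraft treatment site requiring autografting by 3 months". The Study Rationale also states that "The treatment site will be evaluated to assess the progress of wound healing", without giving a scale or a visit.

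The control is within the subject ("The inpatient comparator design allows for a matched control"). The dose regimen section allows "up to two additional applications of StrataGraft skin tissue days 6 through 31, inclusive", after debridement, at the investigator's discretion.

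**The concern.** Each subject has two comparable wounds, one randomized to StrataGraft and one to autograft. Slower closure is a foreseeable price of replacing autograft, and the matched wound looks like the ideal yardstick for it. Yet the visits on days 3 to 28 carry no listed closure score, and the one early treatment-site endpoint has no control counterpart. If every wound is closed at 3 months, the report would show equal closure and say nothing about which site closed first. Adding a score at existing visits seems cheap, and a clinician's closure score not made at the visit cannot be made later.

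**Working it through.** **1. Is closure scored before 3 months?** No: 0 of the 3 closure endpoints, and no early visit in the closure row. If both sites are closed in every pair at 3 months, the discordant shares are b = c = 0 and the paired difference is b − c = 0, whatever happened earlier. With 0 of 20 pairs discordant, the exact 95% upper limit for discordance is 1 − 0.025^(1/20) = 16.8%. The factual premise stands.

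**2. Is 3 months a sound time point?** The objective is to test StrataGraft as an alternative to autografting, working through regeneration of the subject's own tissue. The last permitted application is on day 31. Taking 3 months as day 90, the reading comes at least 90 − 31 = 59 days after the last application. The Study Rationale describes product cells as replaced by the patient's own by three months. So 3 months is the first listed visit at which treatment is over and closure can be expected to mean the patient's own tissue. A deficit lasting that long enters the primary endpoint. A delay that leads to grafting of the StrataGraft site enters the other primary endpoint, which is assessed from day 3.

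**3. What would early readings measure?** The candidate visits are days 14, 21 and 28, and all lie inside days 6 to 31. Two things can happen there at the StrataGraft site:

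- Re-application follows surgical or non-surgical debridement, so a wound scored closed can be reopened by treatment. No equivalent is stated for the autograft site.
- The Test Product section says the product itself covers the wound at once, and the Study Rationale reports that it stays intact and adherent for at least seven days. A closed reading may therefore be product coverage.

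The first can exaggerate a delay. The second can hide or reverse it. An early reading would not cleanly give even the direction of a healing delay.

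**4. How large could the unseen difference be?** The documents give no healing times, and every input here is assumed. The 27 of 28 closure result in STRATA2011 does not help, because there the product "was applied to the deep partial-thickness portion of thermal burns". Assume autograft median 18 days, StrataGraft 24, 28 or 35, 20 pairs, one closure time per site, and no re-application.

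*Exponential times, independent sites.* The share still open at time t is 2^(−t/median).

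| StrataGraft median | Open at day 28, StrataGraft − autograft | Open at day 90, StrataGraft − autograft |
|---|---|---|
| 24 | 44.5 − 34.0 = 10.5 points | 7.4 − 3.1 = 4.3 points |
| 28 | 50.0 − 34.0 = 16.0 points | 10.8 − 3.1 = 7.6 points (unrounded shares) |
| 35 | 57.4 − 34.0 = 23.4 points | 16.8 − 3.1 = 13.7 points |

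*Lognormal times, subject and site log-SD 0.3 to 0.6 (simulated).* The difference is 13 to 55 points at day 28 and 0 to 10 at day 90.

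*What the present schedule keeps.* On visits at days 90, 180 and 365, StrataGraft is first seen closed later than autograft in 0.1 to 12% of pairs and earlier in 0 to 2% (lognormal). Under the exponential model it is 7, 10 and 16% later and about 3% earlier. How much is lost depends on the model assumed.

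*Precision at day 28.* The half-width is 1.96 × √[(b + c − (b − c)²)/n], where b is the share of pairs with only autograft closed and c the share with only StrataGraft closed. For the exponential 18 against 28 case:

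- b = 0.660 × 0.500 = 0.330 and c = 0.500 × 0.340 = 0.170.
- Half-width = 1.96 × √[(0.500 − 0.026)/20] = 0.30, against a difference of 0.16.

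Under this model the half-width is about 30 points at all three medians, wider than each difference in the table, and exact McNemar power is 5 to 20%. Under the lognormal settings the half-width is about 22 to 24 points and the power 7 to 98%.

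**The case for a change.** The best case for the concern needs no simulation. The pairing is the strength of the design. The protocol already expects some StrataGraft sites to need more than one application, and nothing listed says which wound closed first. Days 14, 21 and 28 are existing visits at which a treatment site is already assessed and photographed, so the cost would be a few form fields and perhaps control-site photographs. Results could be labelled descriptive and shown beside re-applications and any grafting.

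Much of this stands. The gap is real in the summary text, the cost is low, and a sponsor could reasonably choose to add such a reading. What does not stand is the step from there to a shortcoming in the plan. No listed endpoint is mis-timed for its purpose, no figure is wrong and no analysis is invalid. Labelling the result descriptive does not cure the problem in step 3, because the reading would still mix product coverage, debridement and healing in one arm only. A subject whose StrataGraft site is autografted before closure also has no obvious place in a later, same or earlier classification, and the results would depend on that choice.

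Two limits temper the claim of absence. The text at hand is the protocol's summary. The early photograph row also does not say which arm's site it covers, so some control-site information may be collected anyway.

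**Conclusion.** The concern does not hold. Closure is indeed scored only from 3 months, and a delay resolved by then gets no paired estimate. That follows from a defensible choice: closure is read once the re-application window has ended and product cells are described as replaced. Following the plan as written gives a sound comparison at 3, 6 and 12 months.

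The amount left unseen cannot be stated from the documents. Under assumed medians it is about 10 to 55 points at day 28, falling to 0 to 14 at day 90. Those figures assume one closure time per site with no re-application or grafting, which the treatment rules do not guarantee. With at most 20 pairs, a modest delay could only be described. An early closure score is a matter of preference, with interpretive problems of its own.

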### Secondary clinical safety assessments

- Treatment-emergent AE assessed throughout study duration
- Incidence of infection assessed at all study sessions
- Vital signs assessed at all study sessions
- Safety laboratory values at baseline, day 7, and day 28
- Immunology assessments at baseline, day 28, and 3 months
- Archival plasma and leukocyte collection at baseline and 3 months
- Persistence of allogeneic DNA at 3 months

### Statistical methods

- Standard statistical measures
- SAS statistical program

### Study Assessments (efficacy)

Assessments	Methods	Schedule of Assessments
Percent area of treatment site requiring autografting	Clinician assessment supported by photodocumentation	Days 3, 7, 14, 21, 28 and 3 months
Wound closure of treatment sites	Clinician assessment supported by photodocumentation	3, 6, and 12 months
Cosmesis of treatment sites	POSAS supported by photodocumentation	3, 6, and 12 months
Cosmesis of donor sites	POSAS supported by photodocumentation	3, 6, and 12 months
Pain of donor sites	Wong-Baker FACES pain rating scale (FPRS)	Days 3, 7, 14, 21, and 28

### Study Assessments (safety)

Assessments	Methods	Schedule of Assessments
Blood chemistry and safety laboratory parameters	CMP and CBC with differential	Baseline, 7 and 28 days and as per SOC
Vital signs	Blood pressure, temperature and pulse	Every study session

Immunological evaluations	Panel reactive antibodies (PRA)	Baseline, 28 days, and 3 months
	Anti-bovine serum albumin (BSA) antibodies	Baseline and 3 months
Incidence of infection	Clinical signs and symptoms; laboratory evidence as necessary	Every study session
Presence of allogeneic DNA	PCR of short tandem repeats	Baseline and 3 months
Adverse events	Standard	Throughout study duration

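### Anti-BSA antibody has one post-exposure sample, at 3 months; a day-28 measurement would catch responses to the initial or an early repeat application that fade before then

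*Combined protocol and SAP*

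**What the plan says.** The row at issue in the Study Assessments (safety) table is "Anti-bovine serum albumin (BSA) antibodies". The table gives the two immunology assays different schedules:

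- "Panel reactive antibodies (PRA) Baseline, 28 days, and 3 months"
- "Anti-bovine serum albumin (BSA) antibodies Baseline and 3 months"

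The list under Secondary clinical safety assessments has a single line for the category, "Immunology assessments at baseline, day 28, and 3 months", and does not say which assays it covers. The same list has "Safety laboratory values at baseline, day 7, and day 28" and "Archival plasma and leukocyte collection at baseline and 3 months". Blood is therefore drawn at day 28 for other purposes, but no plasma is archived then.

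Under Test Product Route of Administration and Dose Regimen, subjects in both cohorts may receive "up to two additional applications of StrataGraft skin tissue days 6 through 31, inclusive". The Study Rationale includes among the safety assessments "incidence of wound infection, and immunologic responses to StrataGraft tissue". The documents supplied give no reason for treating the two assays differently.

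**The concern.** The study objective covers safety of single and multiple applications, and immunologic response to the product is a named safety assessment. For anti-BSA, everything after first exposure is summarised by one value taken well after the application window has closed. A baseline value and one late value can show that antibody is present at 3 months. They cannot show that antibody appeared and then disappeared, or whether it was already present while applications were still being given.

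The same gap affects the interim safety review that decides whether cohort 2 opens. That review follows the fifth cohort 1 subject's 3-month visit, so it can include 3-month anti-BSA results but none between baseline and that visit. Because no day-28 plasma is archived, the plan leaves no stored sample for a retrospective assay.

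**Working it through.** The plan states no figure on this point, so there is none to reproduce. The check compares sampling days with the application window.

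**Inputs from the documents**

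- Anti-BSA: baseline and 3 months (Study Assessments (safety)).
- PRA: baseline, day 28 and 3 months (same table).
- Repeat applications: up to two, days 6 to 31 (Test Product Route of Administration and Dose Regimen).
- Archival plasma: baseline and 3 months (Secondary clinical safety assessments).
- Subjects: up to 20 (Number of Subjects).

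**Assumptions, not in the documents**

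- The first application is on day 0.
- The 3-month visit falls on day T, between 84 and 92.
- A response becomes detectable L = 7 to 14 days after the application that provokes it.

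**Step 1. Number of post-exposure samples.** Anti-BSA has 1 (3 months). PRA has 2 (day 28 and 3 months).

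**Step 2. Time from application to the only post-exposure anti-BSA sample.** For an application on day a, the gap is T − a.

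- First application, a = 0: 84 to 92 days.
- Latest permitted application, a = 31: 84 − 31 = 53 to 92 − 31 = 61 days.

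**Step 3. How long a response must stay detectable to be seen at 3 months.** The minimum duration is T − (a + L).

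| Application day a | Shortest (T = 84, L = 14) | Longest (T = 92, L = 7) |
|---|---|---|
| 0 | 84 − 14 = 70 days | 92 − 7 = 85 days |
| 6 | 84 − 20 = 64 days | 92 − 13 = 79 days |
| 31 | 84 − 45 = 39 days | 92 − 38 = 54 days |

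**Step 4. What a day-28 sample adds.** It splits the unsampled 84 to 92 days into 28 days and 56 to 64 days (84 − 28 and 92 − 28). A response to the day-0 application is then seen if it stays detectable for at least 28 − (0 + L), which is 14 days (L = 14) to 21 days (L = 7), instead of 70 to 85 days. With T = 90, day-0 responses lasting 28, 42 or 56 days are missed by the present schedule and caught with the added sample.

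**Step 5. What it does not add.** A response can be visible at day 28 only if a + L ≤ 28, so a ≤ 21 (L = 7) or a ≤ 14 (L = 14). The sample precedes any application on days 29 to 31 and, on the assumed lag, may also come too early for applications in the preceding week or two. For these the 3-month sample remains the only one. Since repeat application is allowed from day 6, a subject may have had one, two or three applications by day 28.

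**The case against.** The case for leaving the schedule alone has real content.

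- The 3-month sample is a coherent choice. It follows every permitted application, coincides with both primary endpoints and is available to the interim safety review. Adverse events are collected throughout, so clinical consequences of an early response would still be reported. This stands. It argues for keeping the 3-month sample, but does not show what a day-28 value would have found.
- A reader might infer that the assessment list and the table contradict each other. They do not strictly do so: the list names a category, and PRA alone satisfies its day-28 entry. What remains is an ambiguity about whether anti-BSA is meant to be included.
- A reader might put a size on the loss. If the response peaks near day 28, no antigen or antibody production continues, and the half-life is 21 days (range 14 to 28), the fraction left at day 90 is 2^(−62/21) = 13% (5% to 22%). A response about 8-fold above the cut-off (22-fold to 5-fold) could then read negative. Every input is assumed, and the figure fits only a response peaking near day 28. If the peak came 28 days after a day-31 application, on day 59, the fraction left would be 2^(−31/21) = 36% (22% to 46%), or about 2.8-fold. Continuing production would shrink both losses. The documents support neither figure as an estimate.
- The description of the test product does not mention BSA, so exposure is implied only by the sponsor's choice of assay. The documents also give no tube type or volume for the day-28 draw, so use of that blood cannot be taken for granted. Both limits stand.
- The text supplied is the protocol summary. A fuller schedule or rationale elsewhere could not be checked.

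**Conclusion.** The point holds as a modest, inexpensive improvement to a secondary safety assessment. Anti-BSA has one post-exposure sample, 84 to 92 days after first application and 53 to 61 days after the latest permitted one. A response to the initial or an early repeat application that fades before then would be recorded as no response, and the planned archive could not recover it. These intervals rest on day 0 as first application and 3 months as days 84 to 92. The 70 to 85 days of detectability needed for a first-application response rests also on the assumed 7-to-14-day lag.

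A reader might go further and say that the schedule biases anti-BSA incidence downward. Any error from this cause would be in that direction, but whether and how often it occurs is not shown: the documents give no kinetics, and a persistent response would still be seen at 3 months. Nor would a day-28 sample cleanly separate first-exposure from repeat-exposure responses, because subjects may already have been re-treated by then. The primary endpoints are not affected.

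**What to change.** Add day 28 to the anti-BSA row of the Study Assessments (safety) table, which brings it into line with the immunology entry in the assessment list. Use blood from the existing day-28 draw if volume and tube type allow. Keep the 3-month sample.

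Define anti-BSA response as a rise over baseline at day 28 or 3 months. Report it as a per-subject listing with the number and dates of applications before each sample. With at most 20 subjects, a table split by number of applications would have very small cells. State alongside it that the day-28 value does not cover applications on days 29 to 31 and does not fully separate first- from repeat-exposure responses. If the sponsor intends only PRA at day 28, the assessment list should say so and give the reason.

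The cost is up to 20 extra assays (one per subject), one changed table entry, possibly a slightly larger day-28 blood volume, and possibly a higher reported anti-BSA incidence. No new visit is needed. The change only helps subjects whose day-28 blood has not yet been taken, since no plasma is archived at that visit.
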